10.1 Definition of Protocol Deviations and Analysis Sets

No per Protocol analysis is planned.

Important protocol deviations are protocol deviations that might significantly affect the completeness, accuracy, and/or reliability of the study data or that might significantly affect a subject's rights, safety, or well-being.

The following important deviations will be identified and confirmed prior to or at the Data Review Meeting, which will occur before the database lock. The outcome of the Data Review Meeting will document the important protocol deviations as well as the finalization of the analysis population in a memo.

- Subjects that are dosed on the study despite not satisfying the inclusion criteria
- Subjects that develop withdrawal criteria whilst on the study but are not withdrawn
- Subjects that receive the wrong treatment or an incorrect dose
- Subjects that receive an excluded concomitant medication
- Deviation from Good Clinical Practice

- Inclusion and exclusion criteria violations
- Other violations/events that may have a relevant influence on the pharmacokinetic/pharmacodynamic (PK/PD) analysis (eg, adverse events (AEs), vomiting, sample processing errors, inaccurate dosing, etc.)

Any important protocol deviations that lead to the exclusion of a subject from an analysis set will be considered clinically important (see [Section 10.2](#)).

All important protocol deviations should be documented in Clinical Data Interchange Standards Consortium Study Data Tabulation Model (SDTM) (or Analysis Data Model (ADaM) for those derived by programming) whether identified through sites monitoring, medical review and/or programming based on the inclusion/exclusion criteria presented in the protocol. Important protocol deviations to be identified by programming as well as all clinically important protocol deviations are listed and described in [Appendix 3](#).

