10.2 Definition of Analysis Sets and Subgroups

Screening Analysis Set (SCR)

The SCR includes all subjects who signed the informed consent.

Safety Analysis Set (SAF)

The SAF will include all subjects who received at least 1 dose of M2951 or placebo. The SAF will be used for all demographic/baseline characteristics and safety analyses.

Analyses performed on the SAF will consider subjects as treated. Subjects will be allocated to active arm if at least one dose of M2951 was taken during first 12-week treatment period.

The OLE SAF will include all subjects who received at least 1 dose of M2951 during the OLE period. The OLE SAF will be used for all safety analyses at the time of the final analysis.

mITT Analysis Set

The mITT Analysis Set will include all subjects who received at least 1 dose of M2951 or placebo and have at least 1 available ACR20 evaluation at a time point postdose. The mITT Analysis Set will be used for the analysis of all efficacy endpoints. Subjects will be analyzed as randomized.

The OLE mITT Analysis Set will include all subjects who received at least 1 dose of M2951 during OLE period and have at least 1 available efficacy evaluation (ACR components, ESR, anti-CCP, RF) at a time point after first dose in OLE period. The OLE mITT Analysis Set will be used for the analysis of efficacy endpoints at the time of the final analysis.

Pharmacokinetic Analysis Set

The PK Analysis Set will include all subjects who receive at least 1 dose of M2951 and have at least 1 quantifiable M2951 plasma concentration at a scheduled PK time point postdose without any important deviations or events that may impact the quality of the data or alter the evaluation of the PK. The PK Analysis Set will be used for all PK analyses. Subjects who receive placebo will not be included.

Pharmacodynamic Analysis Set

The PD Analysis Set will include all subjects who receive at least 1 dose of M2951 or placebo and have at least 1 measured PD endpoint, not including CCI [REDACTED], at a scheduled PD time point after first dose without deviations or important events affecting PD, and who provide evaluable PD data. All PD analyses, not including CCI [REDACTED], will be based on this analysis set.

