Definition of CFB:

CFB and percent CFB will be computed as follows:

- CFB = visit value – baseline value
- Percent CFB = 100 * (visit value – baseline value) / baseline value

Definition of duration:

Unless otherwise specified, duration will be calculated as the difference between start and stop date + 1 (e.g. duration of AE (days) = AE start date – AE stop date + 1). Unless otherwise specified, missing dates will not be imputed.

The time since an event will be calculated as:

- date of event minus reference date +1 (eg days in study at onset of AE = AE start date - date of randomization + 1) if date of event is equal or greater than reference date
- date of event minus reference date (eg days in study at onset of AE = AE start date - date of randomization) otherwise

Conversion factors:

The following conversion factors will be used to convert days into months or years: 1 month = 30.4375 days, 1 year = 365.25 days. For time windows calculation, 1 month is expressed as 30 days.

Definition of Body Mass Index (BMI) (kg/m²):

BMI will be computed as weight / (height²), where weight is expressed in kg and height in m.

Handling of missing data:

The Table 3 summarizes how missing data will be handled for each ACR component and DAS28-hsCRP:

Table 3: Missing data handling of ACR and DAS28-hsCRP

Period covered	Parameter	Methods of imputation
12-Week treatment period	ACR	
 1. LOCF-NR (Primary analysis): 
 a. Imputation of each component using LOCF b. Derivation of ACR (responder/non-responder) c. If the subject discontinues from treatment, the subject will be considered as non-responder for all visits after discontinuation 2. Non-responder imputation (sensitivity analysis) 
 a. Derivation of ACR (responder/non-responder) using observed ACR components b. If the ACR is missing, then the ACR will be assigned as non-responder 3. Other sensitivity analysis (see Table 13)
	DAS28-hsCRP	LOCF: 
 a. Imputation on each component using LOCF b. Derivation of DAS28-hsCRP at each timepoint
OLE period	ACR	No imputation
	DAS28-hsCRP	No imputation

Unless otherwise specified, missing data will not be replaced.

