	Percentage of subjects with DAS28-hsCRP < 3.2 (well-controlled disease) at Week 12/Day 84	(1) Primary: Computation of response rate, point estimate and 2-sided 80% CI for Δ based on the “corrected Miettinen-Nurminen” method (2) Supportive: logistic regression with treatment and baseline hsCRP as covariate	Primary: LOCF-NR (Table 3)
	Percentage of subjects with DAS28-hsCRP < 2.6 at Week 12 / Day 84	(1) Primary: Computation of response rate, point estimate and 2-sided 80% CI for Δ based on the “corrected Miettinen-Nurminen” method (2) Supportive: logistic regression with treatment and baseline hsCRP as covariate	Primary: LOCF-NR (Table 3)
** All supportive analysis will be based on the primary missing data imputation method. No sensitivity analysis of missing data imputation will be performed for all supportive analyses.			

The Table 13 summarizes the sensitivity analyses to be performed on missing data imputations:

Table 13 : Sensitivity analysis for the primary analysis

Endpoint	Method
ACR Response	
Non-responder imputation (NR): ACR20 response rate will be evaluated on mITT analysis set. Subjects with missing ACR score will be considered as non-responders.

	
Completely Missing at Random pattern (MCAR): ACR20 response rate will be evaluated as observed without any LOCF imputation on mITT analysis set.

	
Missing At Random pattern (MAR): ACR20 will be imputed using multiple imputations process using MI SAS procedure as follows:
 
 1. Monotone missing data structure will be created as follows: intermediate (non-monotone) missing data will be multiply imputed using the Markov chain Monte Carlo (MCMC) method and assuming MAR and multivariate normality. Transformation of data will only be used if there is a clear deviation from normality. The SAS procedure PROC MI with the MCMC option will be used with seed number=20170524. The number of burn-in iterations will be set to 200, which is the default value. Nevertheless, if diagnosis plots show that the convergence has not yet occurred, this will be adjusted. 2. Then, each component will be imputed with treatment group, hsCRP at baseline and data at previous visit from all ACR20 components as covariates. 3. Imputation will be repeated 1000 times. The ACR20 will then be calculated for each of the multiply imputed data sets from the imputed components. Results will be combined using MIANALYZE SAS procedure with the Rubin's rules.

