	
Missing Not At Random pattern (MNAR): ACR20 will be imputed using multiple imputations process with MI SAS procedure for the MNAR pattern, using controlled-arm data with the MNAR statement from SAS MI procedure.

Subgroup analyses will be performed on the randomized subjects with either:

- hsCRP at screening ≥ 3.6 mg/L
- hsCRP at baseline ≥ 3.6 mg/L
- hsCRP at screening ≥ 5 mg/L
- hsCRP at baseline ≥ 5 mg/L

The Table 14 summarizes the analyses to be performed for each subgroup:

Table 14 : Subgroup analysis for the primary analysis

Endpoint	Method	Missing Data Handling
ACR20/ACR50/ACR70 response at each visit	Primary: Computation of response rate, point estimate and 2-sided 80% CI for Δ based on the “corrected Miettinen-Nurminen” method	Primary: LOCF-NR (Table 3)
CFB in hsCRP and DAS28-hsCRP score at Week 4/Day 28 and Week 12/Day 84	Primary : ANCOVA model Supportive: Hodges-Lehmann estimation for 80% CI, only if the assumption of normality is violated	Primary and supportive: LOCF of each component prior to DAS28 calculation
Percentage of subjects with DAS28-hsCRP < 3.2 (well-controlled disease) at Week 12/Day 84	Primary: Computation of response rate, point estimate and 2-sided 80% CI for Δ based on the “corrected Miettinen-Nurminen” method	Primary: LOCF-NR (Table 3)
Percentage of subjects with DAS28-hsCRP < 2.6 at Week 12 / Day 84	Primary: Computation of response rate, point estimate and 2-sided 80% CI for Δ based on the “corrected Miettinen-Nurminen” method	Primary: LOCF-NR (Table 3)

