The 2-sided 80% CI for Δ based on the "corrected Miettinen-Nurminen" method will be computed with SAS® FREQ procedure, using RISKDIFF and CL=MN statements.

The primary analysis will be based on the mITT Analysis Set using post baseline LOCF for imputation of missing values for the ACR components. If a subject discontinued prior to Week 12, then the subject will be considered as ACR20 non-responder. The null hypothesis H0: $\Delta \leq 0$ will be rejected at the 1-sided 0.10 level if the lower limit of the 2-sided 80% CI exceeds zero.

The primary analysis will be repeated for subjects with baseline hsCRP ≥ 3.6 mg/L, as detailed in Table 14.

Additional sensitivity analyses will be performed on ACR20 response as described in Table 13.

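### ACR20 non-response is triggered only by discontinuation, so a protocol-defined treatment failure kept on study drug can count as a responder; a smaller gap in mITT merits one sensitivity row

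*SAP*

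**What the plan says.** **Scoring.** SAP Section 11, Table 3, defines the primary method, LOCF-NR, in three steps. Step a carries each ACR component forward, and step b derives response. Step c reads: "If the subject discontinues from treatment, the subject will be considered as non-responder for all visits after discontinuation". SAP 16.1 repeats it: "If a subject discontinued prior to Week 12, then the subject will be considered as ACR20 non-responder". Neither place gives another trigger for non-response.

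**Treatment failure.** Protocol 6.5.2 classes the start of any new immunosuppressant or immunomodulator as a treatment failure that should end in withdrawal from study drug. Protocol 5.5.1 requires withdrawal for prohibited medication, then adds that the Investigator may give medication needed for the subject's well-being. Protocol 6.5.1 keeps 6.5.2 medicines outside such discretion.

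**Non-withdrawn subjects.** The important deviations in SAP 10.1 include "Subjects that develop withdrawal criteria whilst on the study but are not withdrawn". SAP Appendix 3 (PDEV36) makes a non-permitted drug an important deviation and leaves clinical importance to case-by-case review. Section 10.1 links that term to set membership: "Any important protocol deviations that lead to the exclusion of a subject from an analysis set will be considered clinically important". No per-protocol analysis is planned.

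**Analysis set.** Under SAP 10.2, mITT subjects must have had a dose and "have at least 1 available ACR20 evaluation at a time point postdose". In Table 13 the non-responder row says "ACR20 response rate will be evaluated on mITT analysis set. Subjects with missing ACR score will be considered as non-responders", and the observed-case row also uses mITT. The missing-at-random row ("ACR20 will be imputed using multiple imputations process using MI SAS procedure as follows") and the missing-not-at-random row name no set. The subgroup text says "Subgroup analyses will be performed on the randomized subjects with either", while SAP Table 1 assigns efficacy to mITT.

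**The concern.** **Main point.** A subject who starts a new immunosuppressant and is withdrawn is a non-responder at Week 12. A subject who starts the same drug and stays on study drug is scored on the joint counts and other components, which the new drug may itself have improved. The two are scored differently because of how the site handled withdrawal. The non-responder sensitivity row does not catch the second subject, because the ACR20 is not missing. With about 30 subjects per arm, a few such cases could matter to the comparison that decides the trial. A choice about them made after treatment codes are known would be open to challenge.

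**Minor point.** A dosed subject who leaves before any post-dose ACR20, and also misses the End of Treatment Visit, is outside mITT. Step c would call that subject a non-responder but never reaches them. No planned ACR20 analysis clearly includes the subject.

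**Working it through.** **Inputs.** From protocol 8.1 and SAP 7: 60 mITT subjects randomised 1:1, response 0.46 against 0.21, one-sided 10%, stated power 80.2%, and 64 randomised at 6.25% dropout. SAP 16.1 gives the score interval with factor n/(n−1).

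**Formula.** The lower 80% limit exceeds zero when

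z = (x₁/n₁ − x₂/n₂) / √[ p̂(1−p̂)(1/n₁ + 1/n₂) · N/(N−1) ] > 1.2816,

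where p̂ is the pooled proportion and N = n₁ + n₂. Summing binomial probabilities over all outcomes that meet this gives exact rejection rates.

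**Step 1: the plan's own figures.** With 30 per arm, power is 80.3% (stated 80.2%). The false-positive rate at 21% in both arms is 9.3%. Also 60/(1 − 0.0625) = 64. The plan is reproduced.

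**Step 2: one failure kept on study drug.** One subject is 1/30 = 3.3 points of an arm's rate. Take 21% and 46% as the rates with such failures counted as non-responders. If one case has chance q of being scored a responder, that arm's rate rises by q/30. The documents give no q, so three values are assumed.

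| q | False-positive: active / placebo / random arm | Power: active / placebo / random arm |
|---|---|---|
| 0.21 | 10.46% / 8.27% / 9.36% | 81.87% / 78.50% / 80.18% |
| 0.46 | 11.93% / 7.15% / 9.54% | 83.62% / 76.24% / 79.93% |
| 1 | 15.54% / 5.19% / 10.36% | 86.99% / 71.04% / 79.02% |

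The random-arm figure is the mean of the two arms, for example (10.46 + 8.27)/2 ≈ 9.36. At the planned rates, rescoring one responder as a non-responder changes the decision with probability 8.6% in the active arm or 6.9% in placebo.

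**Step 3: dosed subjects outside mITT.** Assume 32 dosed per arm, with up to four deleted. Four is an upper figure: the 64-to-60 allowance can include subjects never dosed, whom SAP Table 5 counts separately. The result depends on where the 21% is taken to hold.

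- View A: 21% holds among all dosed and deleted subjects are non-responders. With a deleted, an arm's mITT rate is 0.21 × 32/(32 − a).
- View B: 21% holds in mITT, which is how the sample-size text states it. The all-dosed analysis adds the deleted subjects as non-responders, with denominator 32.

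False-positive rates:

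| Deleted active/placebo | A: mITT | A: all dosed | B: mITT | B: all dosed |
|---|---|---|---|---|
| 0/0 | 9.5% | 9.5% | 9.5% | 9.5% |
| 2/2 | 9.3% | 9.3% | 9.3% | 9.3% |
| 4/0 | 15.0% | 9.3% | 9.6% | 5.7% |
| 0/4 | 6.6% | 9.3% | 10.9% | 14.5% |

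Over all splits of up to four, mITT runs from 6.6% to 15.0% under A and stays between 9.3% and 10.9% under B. The all-dosed analysis stays between 9.3% and 9.5% under A and runs from 5.7% to 14.5% under B.

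**The case against.** The main case needs a departure from the protocol. Protocol 5.5.1 says a subject on prohibited medication must be withdrawn, and 6.5.2 says such drugs require stopping study drug. The discretion in 5.5.1 can be read consistently: the medicine may be given and the subject then leaves study drug. Anyone handled that way is already a non-responder. Remaining cases are tabulated and listed as important deviations. The largest figures need a case in one chosen arm that is certain to be scored a responder. All of this stands and keeps the point small. It does not remove it: the SAP itself lists non-withdrawn subjects, and listing a deviation does not say how the subject is scored.

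On mITT, both documents give the same definition for the primary set and the sample size allows for losses. An End of Treatment Visit is required immediately (protocol 5.5.1) or within 5 days (7.1.2.1), so most early leavers stay in. SAP Table 6 shows safety-set and mITT counts by arm, so a reader would see any loss. SAP 10.2 gives all efficacy endpoints to mITT, which by default covers the multiple-imputation rows. This also stands.

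A reader might infer three stronger things that the documents do not support:

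- That the kept-on-drug failure has no scoring rule. Table 3 steps a and b do score that subject; what is missing is a rule for the failure as such.
- That the SAP holds a general principle that treatment failures are non-responders. Its trigger is discontinuation; treatment failure is the protocol's term, tied to withdrawal.
- That LOCF-NR causes the mITT loss. The mITT definition does.

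**Conclusion.** Both gaps are in the text, and closing them is a cheap improvement. The main one is that a protocol 6.5.2 failure kept on study drug can count as an ACR20 responder. One such case is worth at most 3.3 points of an arm's rate. If it falls in the active arm, the false-positive rate goes from 9.3% to between 10.5% and 15.5%. If it falls in placebo, power goes from 80.3% to between 78.5% and 71.0%. In a random arm the false-positive rate stays at 9.4% to 10.4%. These figures rest on 30 per arm and an assumed chance of being scored a responder. The documents give neither the number of cases nor their split by arm, so the direction of any bias is unknown.

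The mITT gap is minor. It would be wrong to conclude that mITT is the biased analysis and all-dosed the sound one: Step 3 shows that either can drift, depending on an assumption the trial cannot verify. Nothing here shows the decisive test to be unsound.

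**What to change.** Before the primary-analysis unblinding:

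1. Extend Table 3 step c and SAP 16.1: a subject who meets the protocol 6.5.2 treatment-failure definition is an ACR non-responder at all later visits, whether or not study drug was stopped. Identify cases at the Data Review Meeting, blind to treatment and by staff who have not seen interim results by arm. Log the change in SAP Section 9.
2. Keep mITT primary. Add one row to Table 13: ACR20 in all randomised and dosed subjects, as randomised, with those lacking a post-dose ACR20 counted as non-responders. Label it a robustness check.
3. State which analysis set the subgroup analyses use and, for completeness, the two multiple-imputation rows.

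The cost is one more table and a few SAP sentences; the dosing and medication data are already collected. Response rates may fall slightly.

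Separately, protocol 5.5.1, 6.5.1 and 6.5.2 must be reconciled on discretionary use of prohibited medicines. Item 1 concerns scoring only, and no clinical rule is proposed.

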16.2 Secondary Endpoint Analyses

16.2.1 Key secondary endpoint analysis

The key secondary endpoint is the change in hsCRP from Baseline to Week 4 and will be presented on the mITT Analysis Set.

Descriptive statistics will be presented by treatment group for CFB as well as percent CFB of hsCRP. A point estimate and 2-sided 80% CI for the difference Δ in Week 4 hsCRP mean CFB between subjects treated with M2951 + MTX and subjects treated with placebo + MTX (reference) will be provided.

Point estimate and its CI limits will be estimated with SAS® GLM procedure using LSMEANS statement. The ANCOVA will include baseline as a covariate and treatment group as an independent variable. A sensitivity analysis will be performed using a non-parametric method. The Hodges-Lehmann difference median estimate and 80% CI will be calculated with SAS® NPAR1WAY procedure using HL statement. Asymptotic and exact CIs will be computed.

Assumptions for the ANCOVA models:

Validity of the model will be verified as follows:

- The homogeneity of variances between treatment groups will be checked using the Levene's test. A scatter plot of residuals versus fitted values will be also performed.
- In order to assess the independence of error terms, a residual lag plot will be performed, ie constructed by plotting residual (i) against residual (i-1).
- A scatter plot of the response variable against the covariate, using separate symbols for each treatment group will be performed to verify the presence of linear relationship between the covariate and the response variable, and that all treatment regression lines have the same slope.
- Homogeneity of regression slopes will be verified by first running the model with the interaction between the covariate and the treatment group. This assumption will be validated if this interaction is not significant. If this assumption is verified, then the interaction will be removed from the model.
- Normality of residuals will be checked by computing Skewness and Kurtosis, which should fall within the interval [-2;2]. Normal QQ-plot of residuals will be performed as well.

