4.2 Key Secondary Objective

To assess the level of disease activity at 4 weeks in subjects with active RA as assessed by the percent change in high-sensitivity C-reactive protein (hsCRP) from Baseline to Day 29.

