An IA will be conducted when subjects from the first 50% of the planned enrollment have reached Day 29 of treatment and have available Day 29 hsCRP data and DAS28-hsCRP data, or have discontinued treatment prior to Day 29. Point and CI estimates of the Day 29 hsCRP change from Baseline difference, comparing the 2 treatment groups, will be estimated for use in internal decision making. A similar analysis of Day 29 DAS28-hsCRP will be performed. The IA will not be used to alter the design of the trial. No adjustment will be made to the 1-sided α of 10% to be used in the primary analysis at the end of the 12-week blinded treatment period.

A final analysis will be conducted at the end of the trial when all subjects have completed the Safety Follow-up visit or prematurely discontinued from study.

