8.3.2 Secondary Endpoints

The key secondary endpoint is the percent change in hsCRP from Baseline to Day 29.

Other secondary endpoints (during the double-blind treatment period):

Efficacy:

- ACR50/ACR70 response at each time point assessed
- Percent change in hsCRP from Baseline to Day 85
- Change from Baseline in DAS28-hsCRP score at Day 29
- Change from Baseline in DAS28-hsCRP score at Day 85
- Percentage of subjects with DAS28-hsCRP < 3.2 (well-controlled disease) at Day 85
- Percentage of subjects with DAS28-hsCRP < 2.6 at Day 85
- Change from Baseline in ESR, anti-CCP, rheumatoid factor (at Days 29 and 85)
- Change from Baseline to Day 85 in subject's self-assessments including:
 - Global assessment of disease activity (VAS, see Section 7.3.1.1)

- Self-assessment of pain (VAS)
- Self-assessment of disability (HAQ-DI)
- Change from Baseline to Day 85 in Physician's Global Assessment of Disease Activity (VAS).

Safety:

- Nature, incidence and severity of TEAEs
- Change from Baseline in vital signs and 12-lead ECG data
- Change from Baseline in standard hematology and chemistry laboratory parameters including liver function tests, amylase/lipase, and urinalysis.

Pharmacokinetics and pharmacodynamics:

- Plasma concentrations of M2951 after administration on Day 1 and Day 29, PK parameters calculated for Day 1 and Day 29: AUC_{0-6h} , C_{max} , C_{pre} (Day 29), t_{max} , $R_{acc}(AUC_{0-6h})$, and $R_{acc}(C_{max})$. Further endpoints may be defined in the SAP.
- Absolute concentrations and change from Baseline in immunoglobulin levels (IgA, IgM, and IgG, and subclasses) on Day 29 and Day 85
- Absolute numbers and change from Baseline in B cell numbers and subsets on Day 85.

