8.5.3 Analysis of Secondary Endpoints

8.5.3.1 Efficacy Endpoints

Descriptive statistics for the percent change in hsCRP from Baseline to Day 29 will be presented by treatment group. A point estimate and 2-sided 80% CI for the difference Δ in Day 29 hsCRP change from Baseline between subjects treated with M2951+MTX and subjects treated with placebo + MTX will be provided.

The Day 85 hsCRP change from Baseline will be analyzed in the same way as the Day 29 hsCRP change from Baseline. This analysis will also be applied to Day 85 DAS28-hsCRP score change from Baseline.

- The Day 85 ACR50 and ACR70 proportions will be analyzed in the same way as the Day 85 ACR20 proportions. This analysis will also be applied to Day 85 “DAS28-hsCRP < 3.2 ” proportion and Day 85 “DAS28-hsCRP < 2.6 ” proportion.

The ACR20/50/70 proportions and proportion of subjects achieving DAS28-hsCRP < 3.2 (well-controlled disease) or DAS28-hsCRP < 2.6 will be tabulated by treatment group and time point.

Descriptive statistics will be tabulated by treatment group and time point for the following continuous variables, both absolute value and change from baseline: DAS28-hsCRP score, hsCRP,

ESR, anti-CCP, and rheumatoid factor, subject's global assessment of disease activity, subject's assessment of pain, subject's self-assessment of disability (HAQ-DI), and Physician's Global Assessment of Disease Activity.

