8.2 Interim Analysis

An IA will be conducted with the percent change in hsCRP from Baseline to Day 29 as key endpoint evaluated at the IA. Details of the statistical analyses of the IA are provided in the IDMC/IA SAP.

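### The key secondary endpoint is named as percent change in hsCRP to Day 29, but every between-group hsCRP estimate in the SAP is on absolute change in mg/L

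*SAP*

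**What the plan says.** **Name of the endpoint.** Protocol 4.2 sets the key secondary objective "as assessed by the percent change in high-sensitivity C-reactive protein (hsCRP) from Baseline to Day 29". Protocol 8.3.2 repeats it: "The key secondary endpoint is the percent change in hsCRP from Baseline to Day 29". SAP Section 6 carries the same sentence. SAP 8.2 uses the percent scale for the interim look: "An IA will be conducted with the percent change in hsCRP from Baseline to Day 29 as key endpoint evaluated at the IA".

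**What the SAP analyses.** SAP 16.2.1 says instead: "The key secondary endpoint is the change in hsCRP from Baseline to Week 4". It places the point estimate and 2-sided 80% interval on the difference in mean CFB from an ANCOVA with baseline as covariate, with a Hodges-Lehmann estimate as sensitivity analysis. The key secondary row of Table 12, the Week 12 analysis in 16.2.2 and the subgroup row of Table 14 also use CFB. Percent CFB is summarised by arm in 16.2.1 and 16.2.2, shown in box plots, and summarised at Month 6 of the extension in 16.3.1.

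**Where the split starts.** Protocol 8.5.3.1 first says: "Descriptive statistics for the percent change in hsCRP from Baseline to Day 29 will be presented by treatment group". Its next sentence puts the point estimate and interval on the difference in "hsCRP change from Baseline between subjects treated with M2951+MTX and subjects treated with placebo + MTX will be provided". The interim text in Protocol 8.1 is worded the same way: "Point and CI estimates of the Day 29 hsCRP change from Baseline difference, comparing the 2 treatment groups". SAP Section 9 describes the ANCOVA on mean changes as added detail and says percent change will be given as summary statistics.

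**The concern.** A named key secondary endpoint should have a planned treatment comparison on its own scale. Here the SAP estimates a different variable and still carries the original name in its trial summary, so a report could present an mg/L difference as the result for a percent-change endpoint. The two measures weight subjects differently. Absolute change is driven by subjects with high baseline hsCRP, while percent change gives a low-baseline subject the same weight as a high-baseline one.

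A reader could subtract the by-arm percent means, but that difference would be unplanned, would have no planned interval, and would be unadjusted for baseline. It might also rest on different data: the percent summaries in Table 12 and 16.2.2 are as observed, while the key secondary estimate uses LOCF.

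A Sponsor subteam sees 4-week hsCRP results by arm at the interim (Protocol 6.10). That is a further reason for an explicit, dated record of which scale was chosen. Nothing in the documents suggests that interim data influenced the choice.

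**Working it through.** **No hsCRP figure to reproduce.** The documents give no standard deviation, effect size, power or test for hsCRP. The only power figure is 80.2% for ACR20 (SAP Section 7). Exact enumeration with 30 per arm, response 0.46 against 0.21, and the score interval with factor 60/59 gives 80.3%. That figure stands and has no bearing on this point.

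**Step 1: are the two terms distinct in the SAP?** Section 11 introduces them together, "CFB and percent CFB will be computed as follows", then gives two formulas:
- CFB = visit − baseline
- percent CFB = 100 × (visit − baseline) / baseline

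Section 16.2.1 also asks for descriptive statistics on each. CFB therefore cannot be read as shorthand for percent CFB.

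**Step 2: count the between-group hsCRP estimates.**

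| Source | Estimates | On percent CFB |
|---|---|---|
| Week 4, full set (16.2.1, Table 12): ANCOVA, Hodges-Lehmann | 2 | 0 |
| Week 12, full set (16.2.2, Table 12): same two methods | 2 | 0 |
| Table 14: 4 subgroups × 2 visits, ANCOVA | 8 | 0 |
| **Firmly planned** | **12** | **0** |
| Table 14: 4 × 2 Hodges-Lehmann, only if normality fails | 8 | 0 |
| **Maximum** | **20** | **0** |

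**Step 3: does the scale matter?** A fall of 2 mg/L is 2/3.6 = 55.6% at the entry limit (inclusion criterion 5). At an assumed baseline of 20 mg/L it is 2/20 = 10%.

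**Step 4: can the direction change?** This example uses assumed values, not trial data. There are 30 subjects per arm, 15 with baseline 4 mg/L and 15 with baseline 40 mg/L in each arm.

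| | Baseline 4 | Baseline 40 | Mean CFB | Mean percent CFB |
|---|---|---|---|---|
| Arm A | 4 → 2 (−2; −50%) | 40 → 40 (0; 0%) | (−2 + 0)/2 = −1 | (−50 + 0)/2 = −25 |
| Arm B | 4 → 4 (0; 0%) | 40 → 30 (−10; −25%) | (0 − 10)/2 = −5 | (0 − 25)/2 = −12.5 |

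- Absolute, A minus B: −1 − (−5) = **+4 mg/L**, so B looks better.
- Percent, A minus B: −25 − (−12.5) = **−12.5 points**, so A looks better.
- ANCOVA: the baselines are identical in the two arms, so the adjusted differences equal the raw ones, +4 and −12.5.
- Hodges-Lehmann, absolute: the pairwise differences are −2, 0, 8 and 10 in equal numbers; the median is (0 + 8)/2 = +4.
- Hodges-Lehmann, percent: the pairwise differences are −50, −25, 0 and 25 in equal numbers; the median is (−25 + 0)/2 = −12.5.

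Both planned methods reverse sign with the scale. This shows that a reversal is possible. It says nothing about how often it would happen.

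**The case against.** The strongest reply is that the SAP only follows the protocol. Protocol 8.5.3.1 describes percent change by arm and, read literally, puts the estimate on change. SAP Section 9, under its heading on changes to planned analyses, tells the reader exactly what will be estimated. On this view all that remains is a label carried over from the synopsis. This stands in part: the ambiguity does begin in the protocol, and the methods are disclosed. But Section 9 presents them as added detail and never says that the key secondary endpoint changed, although it openly labels other changes, such as the extension mITT definition and the interim trigger. Section 6 still names percent change, so the SAP disagrees with itself.

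Other objections narrow the point:
- The key secondary endpoint is one visit in the full set, so the count that bears on it directly is 0 of 2. The counts of 12 and 20 describe all hsCRP comparisons in the SAP.
- The worked example has a strong treatment-by-baseline interaction, which the slope check in 16.2.1 is designed to flag. It is a demonstration, not a forecast.
- Hodges-Lehmann on percent change would also be unadjusted for baseline. ANCOVA on percent change is adjusted but more exposed to skewness. The choice is a judgement, which is why one should be named in advance.
- No gatekeeping or stated test depends on hsCRP, so the consequence is limited.

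**Conclusion.** The concern holds. Followed exactly, this SAP produces no between-group estimate or interval for the endpoint it names as key secondary: 0 of 2 at Week 4 in the full set, 0 of 12 firmly planned hsCRP comparisons, and 0 of 20 if every conditional one is triggered. That conclusion rests on the text alone. The illustration of reversal rests on assumed values, and no frequency of disagreement is claimed because the documents give no hsCRP distribution.

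The effect is on interpretation of the key secondary result. The ACR20 analysis, its power and type I error are untouched. The interim analysis is specified in a separate SAP that is not among these documents, so nothing is concluded about it. This should be fixed, but it does not threaten the trial's main conclusion.

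**What to change.** **If percent change is intended:**
- Restore the term in SAP 16.2.1 and in the key secondary row of Table 12.
- Add a between-group estimate with a 2-sided 80% interval for Week 4 percent CFB, computed from the same LOCF hsCRP value. Use either Hodges-Lehmann on percent CFB, which copes better with skewed percentages, or the existing ANCOVA applied to percent CFB, which keeps the baseline adjustment. Name one as the main estimate before the treatment codes are broken for the primary analysis.
- Do the same at Week 12 for consistency.
- Keep the mg/L analyses as supportive and record the change in Section 9.
- ANCOVA on ln(visit/baseline), reported as a ratio of geometric means, is an optional supportive analysis.

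**If absolute change is intended:** say in Section 9 that the key secondary endpoint was changed and why, and align Section 6.

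**Cost.** The first route needs text edits in three places and one added estimate at each of two visits. Percent CFB is already derived (Section 11), LOCF for hsCRP is already specified (Section 9), and both procedures are already in 16.2.1. The headline effect would then be in percentage points instead of mg/L. The second route needs wording only.
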